#### 8.1.4 Noninferiority for the Omicron XBB.1.5 subvariant on Day 29 for GMT

Together with the noninferiority of immune response for influenza vaccine strains, SARS-CoV-2 neutralizing antibody responses against Omicron XBB.1.5 subvariant on Day 29 after co-administration of ARCT-2303 and Flucelvax Quadrivalent will be compared to immune response after standalone administration of ARCT-2303

$$\text{GMT ratio} = \frac{\text{GMT}_{\text{QIV+ARCT-2303(Day 29)}}}{\text{GMT}_{\text{ARCT-2303+Placebo (Day 29)}}}$$

The analysis of the GMT ratio will be done using ANCOVA, as described in Section 3.3.2. Non-inferiority will be concluded if the lower limit of the 2-sided 95% CI for the GMT ratio is higher than 0.67.

#### 8.1.5 Super superiority for the Omicron XBB.1.5 subvariant on Day 29 for GMT

Using the same analysis as Section 8.1.1, super superiority of ARCT-2303 to ARCT-154 in terms of neutralizing antibodies GMTs against Omicron XBB.1.5 subvariant will be demonstrated if the lower limit of the 2-sided 95% CI for GMT ratio is higher than 1.5.

#### 8.1.6 Superiority for the Omicron XBB.1.5 subvariant on Day 29 for the difference of SCR

Using the same analysis as Section 8.1.2, superiority of ARCT-2303 to ARCT-154 in terms of neutralizing antibodies SCR against Omicron XBB.1.5 subvariant will be demonstrated if the lower limit of the 2-sided 95% CI for difference of SCRs is higher than 0%.

### 8.2 Descriptive Summaries

Results from VNA assay will also be summarized using descriptive statistics for the following parameters:

- Geometric mean titer (GMT) on Days 1, 29 and 181;
- Geometric mean-fold rise (GMFR) as increases of the post-vaccination titer over the pre-vaccination titer;
- Seroconversion rate (SCR) on Day 29 as the percentage of participants in each arm with either:
  - A pre-vaccination titer below the lower limit of quantitation (LLOQ) and a post-vaccination titer  $\geq 4 \times \text{LLOQ}$ ; or
  - A pre-vaccination titer  $\geq \text{LLOQ}$  and a  $\geq 4$ -fold increase in post-vaccination titer.
- Proportion of participants with antibody titer  $\geq \text{LLOQ}$  on Days 1 and 29.

The results of HI and MN will be summarized using descriptive statistics for the following parameters:

- Geometric mean titer (GMT) on Days 1 and 29.
- Geometric mean-fold ratio (GMFR) as increases of the post-vaccination titer over the pre-vaccination titer.
- SCR on Day 29 as the percentage of participants in a group with either:
  - A pre-vaccination titer below the LLOQ for the respective assay and a post-vaccination titer  $\geq 4 \times \text{LLOQ}$ .
  - A pre-vaccination titer  $\geq \text{LLOQ}$  and a  $\geq 4$ -fold increase in post-vaccination titer.
- Proportion of participants with HI titer  $\geq 1:10, 1:20, 1:40, 1:80, 1:160$  and  $1:320$  on Days 1 and 29.

- Proportion of participants with MN titer  $\geq 1:10$ , 1:20, 1:40, 1:80, 1:160 and 1:320 on Days 1 and 29.

There is no formal hypothesis testing for evaluating the co-administration of ARCT-2303 and Fluad Quadrivalent. The results of the analysis will be presented as described above.

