| 
3. To assess the immunogenicity of ARCT-2303 vaccine when administered with or without Flucelvax Quadrivalent, as measured by virus neutralization assay
 | 
SARS-CoV-2 neutralizing antibody responses against Omicron XBB.1.5 subvariant on Days 1, 29, and 181 (a subset of samples):
 
 • Co-admin group recipients (Group 1a) • Standalone ARCT-2303 group recipients (Group 2a) | 
 • GMTs • GMFRs (post/pre-vaccination) • SCRs^b • Proportion of participants with antibody titer \geq LLOQ 
by PP set for immunogenicity.
 |

CONFIDENTIAL

Table 4 Objectives, Endpoints and Estimands

| | | |
|--|---|---|
| 4. To assess the immunogenicity of Flucelvax Quadrivalent when administered with or without ARCT-2303 as measured by HI assay ^c | 
HI assay titers against influenza vaccine strains on Day 1 and Day 29, in:
 
 • Co-admin group recipients (Group 1a) • Standalone Flucelvax Quadrivalent group recipients (Group 3a) | 
 • GMTs • SCRs • GMFRs (post/pre-vaccination) • Proportion of participants with HI titer $\geq 1:40$ 
For each influenza vaccine strain, by PP set for immunogenicity.
 |
| 5. To assess the immunogenicity of ARCT-2303 vaccine, when administered with or without Fluad Quadrivalent, as measured by virus neutralization assay, in participants ≥ 65 years of age. | 
SARS-CoV-2 neutralizing antibody responses against Omicron XBB.1.5 subvariant on Days 1, 29, and 181:
 
 • Co-admin group recipients (Group 1b) • Standalone ARCT-2303 group recipients (Group 2b) | 
 • GMTs • GMFRs (post/pre-vaccination) • SCRs^b • Proportion of participants with antibody titer \geq LLOQ 
by PP set for immunogenicity.
 |
| 6. To assess the immunogenicity of Fluad Quadrivalent when administered with or without ARCT-2303 as measured by HI assay, ^c in participants ≥ 65 years of age | 
HI assay titers against influenza vaccine strains on Day 1 and Day 29, in:
 
 • Co-admin group recipients (Group 1b) • Standalone Fluad Quadrivalent group recipients (Group 3b) | 
 • GMTs • SCRs • GMFRs (post/pre-vaccination) • Proportion of participants with HI titer $\geq 1:40$ 
For each influenza vaccine strain, by PP set for immunogenicity.
 |
| Secondary Safety Objectives | | |

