Abbreviations: AE, adverse event; AESI, adverse event of special interest; GMFR, geometric mean fold rise; GMT, geometric mean titer; HI, Hemagglutination Inhibition; LLOQ, lower limit of quantification; MAAE, medically attended AEs; MN, microneutralization; PP, per protocol; QIV, quadrivalent influenza vaccine; SAE, serious adverse event; SARS-CoV-2, severe acute respiratory syndrome coronavirus 2; SCR, seroconversion rate; VNA, virus neutralization assay.

^a As per FDA guidance: “simple” superiority (margin of >1 -fold for GMT ratio); “super” superiority (margin of >1.5 -fold for GMT ratio). US FDA Guidance for Industry. Emergency Use Authorization for Vaccines to Prevent COVID-19. Document issued on March 31, 2022.

^b SCR will not be performed on Day 181.

^c In case of lack of agglutination for a specific strain using HI assay, immunogenicity for that strain will be assessed as measured by microneutralization (MN) assay as an acceptable alternative.

Seroconversion rate (SCR) is defined as the percentage of participants with a ≥ 4 -fold increase in titer from that at Day 1 (or from LLOQ if Day 1 titer $<$ LLOQ). For definitions of the PP set for immunogenicity and other populations for analysis, refer to Section 10.3 of protocol.

CONFIDENTIAL

May not be used, divulged, published or otherwise disclosed without written consent of Arcturus Therapeutics, Inc.

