| Secondary | 
For HI assay titers against influenza vaccine strains and for SARS-CoV-2-neutralizing antibodies, the following analyses will be performed:
 
5. Difference in SCRs of $QIV_{QIV+ARCT-2303}$ minus $QIV_{QIV+Placebo}$ (Day 29) and 95% CI by PP set for immunogenicity.6. Difference in SCRs of $ARCT-2303_{QIV+ARCT-2303}$ minus $ARCT-2303_{ARCT-2303+Placebo}$ and 95% CI by PP set for immunogenicity. 
Seroconversion rate and its two-sided 95% CI for each group will be calculated using the Clopper-Pearson method. The difference of seroconversion rates between the two groups and its two-sided CI will be calculated using the Miettinen and Nurminen method. Stratification factors may be applied to calculate the SCR difference, which will be described in the SAP.
 |
| Secondary | 
For VNA on Days 1, 29 and 181, the following analysis will be produced:
 
• GMT and 95% CI;• GMFR and 95% CI;• Number and proportion of participants with seroconversion (SCR) and 95% CI; |

CONFIDENTIAL

- Proportion of participants with antibody titer above LLOQ and 95% CI

For HI assay titers against influenza vaccine strains on Days 1 and 29, the following analysis will be produced:

- GMT and 95% CI;
- GMFR and 95% CI;
- Number and proportion of participants with seroconversion (SCR) and 95% CI;
- Proportion of participants with HI titer $\geq 1:40$ and 95% CI

Geometric mean will be calculated as the mean of the antibody results after the data are log-transformed and then taking the antilog of the log-mean to present the results on the original scale. Two-sided 95% CI will be obtained by taking the log transform of the antibody results and calculating based on t-distribution; then taking the antilog of the confidence limit.

GMFR analysis will include participants with antibody results available at both baseline (prior to Dose 1) and post-vaccination. It will be calculated as the mean of the difference after log-transformed results (post baseline minus baseline) and taking the antilog of the mean. Two-sided 95% CI will be obtained by taking the log transform of the antibody results and calculating the 95% CI based on Student's t-distribution for the mean difference after the data are log-transformed, then taking the antilog of the confidence limit.

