		
both Day 1 to Day 57 and Day 1 to EOS will be summarized.
 
Section 7.1 Solicited AEs: Addition of summaries for the solicited AEs during 7 days post Day 1 vaccination for Groups 2a and 2b combined, Groups 3a and 3b combined.
 
Handling of implausible data collected in eDiary, and analysis of reported symptoms from different arms on different days for one subject, which were decided and documented prior to any planned analysis.
 
Section 7.2 Unsolicited AEs: Addition of summaries for unsolicited AEs, related unsolicited AEs, and SAE 28 days post Day 1 vaccination for Groups 2a and 2b combined, Groups 3a and 3b combined.
 
Section 8.2 Descriptive Summaries: Removal of proportion of <math>\geq</math>LLOQ at Day 181 consistent with the planned analysis.

--	--	---

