## **9 CHANGES TO THE PLANNED ANALYSIS**

Not applicable.

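### SAP 8.2 drops the Day 181 proportion of participants with an XBB.1.5 neutralizing titer at or above LLOQ, which protocol version 2.0 still requires

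*SAP*

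**What the plan says.** **Protocol version 2.0.** In Table 4 (Section 3), the endpoint of secondary objective 3 is "SARS-CoV-2 neutralizing antibody responses against Omicron XBB.1.5 subvariant on Days 1, 29, and 181 (a subset of samples"). Objective 5, for participants aged 65 and over, has the same days. The estimand column for both lists GMT, GMFR, SCR and "Proportion of participants with antibody titer" at or above LLOQ. One footnote limits what is done at the last visit: "SCR will not be performed on Day 181". Table 9 (Section 10.3.2) opens its list of secondary neutralization summaries with "For VNA on Days 1, 29 and 181, the following analysis will be produced" and includes the proportion above LLOQ with a 95% CI. Table 6 (Section 8.10.1) plans Day 181 XBB.1.5 testing in random subsets of 100 from Group 2a and 100 from Group 2b, to assess persistence.

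**SAP version 3.0.** Section 8.2 keeps "Geometric mean titer (GMT) on Days 1, 29 and 181" but then gives "Proportion of participants with antibody titer $\geq \text{LLOQ}$ on Days 1 and 29". The Document History entry for this version records the removal of the proportion at or above "LLOQ at Day 181 consistent with the planned analysis". Section 9, where changes to the planned analysis belong, reads "Not applicable". Section 4.1.4 defines a PP (Day 181) set whose members must have a Day 181 XBB.1.5 result.

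**The concern.** The protocol decided which parameter to leave out at Day 181, and it left out seroconversion only. The SAP leaves out a second one, says this matches the plan, and declares no departure.

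Protocol 2.2.1 states that the duration of the response is unknown and that persistence will be assessed at six months. For that question, the share of participants who still have quantifiable antibody is the natural companion to the mean titer. Without it, Day 181 is described by GMT and GMFR alone, and neither shows how many participants have fallen below the limit. A removal classed as agreeing with the plan may also go unmentioned in the CSR, because SAP 10 promises documentation only for deviations from the planned analysis.

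**Working it through.** The documents give no figure for this endpoint, so there is nothing to reproduce. The check compares the current texts and then asks what the missing summary would have delivered.

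**1. Days for each neutralization parameter.**

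| Parameter | Protocol Table 4 with its footnote | SAP 8.2 |
|---|---|---|
| GMT | 1, 29, 181 | 1, 29, 181 |
| GMFR | post-vaccination, 181 not exempted | no day stated; SAP 8 covers all available time points |
| SCR | 29 (181 exempted) | 29 |
| Proportion at or above LLOQ | 1, 29, 181 (not exempted) | 1, 29 |

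Only the last row conflicts.

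**2. Whether another SAP sentence restores it.** The general statement in SAP 8 on all available time points names GMT, GMFR and SCR. It does not name this proportion, and the specific limit in 8.2 would prevail in any case.

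**3. Whether the data will exist.** Yes: 100 + 100 planned Day 181 titers (protocol Table 6), and an analysis set built on them (SAP 4.1.4).

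**4. Whether GMT can stand in.** SAP 3.6 and 8 set titers below LLOQ to 0.5 × LLOQ. Let p be the proportion at or above LLOQ and m the mean log2 of titer/LLOQ among those participants. Then

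log2(GMT/LLOQ) = (1 − p) × (−1) + p × m.

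One equation cannot fix both p and m. A constructed example:

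- p = 1, m = 1 gives 1, so GMT = 2 × LLOQ.
- p = 0.8, m = 1.5 gives 0.2 × (−1) + 0.8 × 1.5 = 1.0, so GMT is again 2 × LLOQ.

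The same Day 181 GMT is compatible with none or with 20% of participants below the limit. GMFR uses the same imputed values and has the same gap.

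**5. Precision if restored.** The protocol names Clopper-Pearson for titer-threshold percentages. With x of n at or above LLOQ:

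- lower limit = 2.5% quantile of Beta(x, n − x + 1)
- upper limit = 97.5% quantile of Beta(x + 1, n − x)

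The true proportion is not given anywhere, so a range is assumed:

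| Assumed proportion | n = 100 (one group) | n = 200 (2a + 2b) |
|---|---|---|
| 50% | 39.8% to 60.2% | 42.9% to 57.1% |
| 80% | 70.8% to 87.3% | 73.8% to 85.3% |
| 90% | 82.4% to 95.1% | 85.0% to 93.8% |
| 95% | 88.7% to 98.4% | 91.0% to 97.6% |

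Per group the interval is about 10 to 20 percentage points wide, which is adequate for a descriptive statement on persistence.

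**The case against.** The strongest reply is that the protocol is loose here rather than plainly contrary. The day heading in Table 9 also covers SCR, which the footnote excludes at Day 181, and GMFR, which cannot exist at Day 1; it is not a day-by-parameter schedule. The parameter lists in the synopsis and Section 8.10 attach days to GMT and SCR but none to this proportion. The removal is also logged openly in the SAP history. It concerns one untested descriptive summary, Day 181 GMT and GMFR remain, and a tabulated minimum or the individual listings could reveal that some titers fell below LLOQ.

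Part of this stands. Table 9 alone would be weak support, the change was not hidden, and nothing confirmatory depends on it. But Table 4 with its footnote is specific: one parameter is exempted from Day 181, and it is not this one. Section 8.10 also limits the HI and MN titer proportions to Days 1 and 29 and places no such limit on the neutralization proportion. A minimum shows that at least one titer was low, not how many, and gives no interval.

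Three limits on the remedy also stand:

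- Table 6 plans no Day 181 neutralization testing in Groups 1a or 1b. Restoring the summary therefore describes standalone ARCT-2303 recipients only, not the with-or-without comparison named in objectives 3 and 5.
- PP (Day 181) excludes infections and exclusionary deviations, so n may be below 100 per group.
- Pooling the subsets weights the age cohorts 1:1, whereas enrolment in 2a and 2b is 400:160.

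**Conclusion.** The concern holds. Followed as written, SAP 8.2 omits a descriptive secondary estimand that protocol version 2.0 specifies for Day 181. The stated rationale does not match that protocol, and SAP 9 does not declare the difference. The omission affects both Day 181 subsets, 100 participants each as planned. The assumed proportions serve only to show precision; the finding itself rests on the text and on no numerical assumption.

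The consequence is moderate: persistence is reported with less information than planned, while the hypotheses, error control and power are unchanged. SAP version 3.0 is dated 18 December 2024. The documents do not date the Day 57 analysis, so whether the removal came before or after group-level results were known cannot be settled here. Some other entries for that version say they were decided before any planned analysis; this one does not.

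**What to change.** In SAP 8.2, extend the bullet on the neutralization proportion at or above LLOQ to Days 1, 29 and 181. For Day 181, specify n/N, percentage and Clopper-Pearson 95% CI on PP (Day 181), separately for Groups 2a and 2b. If a combined figure is wanted, state that the two subsets contribute equally and so do not reflect the 400:160 enrolment. State also that no Day 181 result is available for Groups 1a and 1b.

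If the sponsor prefers to keep the removal, SAP 9 and the CSR should record it as a departure from protocol Tables 4 and 9, with the reason and its date relative to the Day 57 unblinding. The history wording should be corrected accordingly.

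The cost of restoring the summary is one edited bullet and one table, using titers already planned. No new samples, assays or analysis set are needed.

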## **9 CHANGES TO THE PLANNED ANALYSIS**

Not applicable.

## 10 FINAL ANALYSES

The results of this study will be released sequentially in two separate final analyses.

The two final analyses will be based on the final version of the SAP. Any deviations from the planned analysis will be documented in the CSR.

### 10.1 First Final Analysis

The first final analysis will include all immunogenicity data (up to Day 29), reactogenicity data (7 days post-vaccination), unsolicited AEs (28 days post-vaccination), and safety data collected from Day 1 to Day 57 and associated primary and secondary objectives. This analysis will be conducted on cleaned and frozen data. The results of this analysis will be presented in the initial clinical study report (CSR). Immunogenicity and safety data will be reported on a group level only. No individual listings will be generated. Access to participant-level information about study groups will be restricted to specified personnel involved in the statistical analysis.

### 10.2 Second Final Analysis

The second final analysis of immunogenicity and safety data collected from Day 57 to the study end will be performed as soon as all data are available. For SAE, MAAE, AESI and AEs leading to discontinuation that will be reported cumulatively (ie from Day 1 to end of study as well). The results of this analysis will be presented in the final CSR. All individual data listings with information on participant study group will be presented in the addendum to the CSR.

## **11 SOFTWARE**

- SAS® Version 9.4 or higher (SAS Institute, Cary, North Carolina, USA).

## 13 APPENDIX

### 13.1 Sample Size Calculation

#### **STEP 1**

Objective 1:

The coprimary objective of simple superiority of the ARCT-2303 vaccine booster (groups 2a and 2b) compared to the ARCT-154 booster for the Omicron XBB.1.5 subvariant

Superiority of  $GMT_{ARCT-2303 \text{ (booster)}}$  to  $GMT_{ARCT-154 \text{ (booster)}}$

The superiority margin for the Omicron XBB.1.5 subvariant is defined as 1.0 for the GMTs ratio, thus the lower limit of the 2-sided 95% CI for GMT ratios (ARCT-2303/ARCT-154) is higher than 1.0.

Statistical power for the coprimary objective 1 is calculated assuming that:

- the GMT ratio between ARCT-2303 (Day 29) and ARCT-154 (booster; ARCT-154-J01 study) (Day 29) groups is 1.5,
- the common standard deviation is expected to be 0.60 in the log10 scale.

If the GMT ratio is 1.5 that means that the difference of the 2 means in log scale is 0.176 ( $\delta$ ). The differences between those two means is equal to 0 (=SM) when the GMT ratio is equal to 1.

Numeric Results for an Equal-Variance T-Test

Solve For:	Power						
Difference:	$\delta = \mu_1 - \mu_2 = Mt - Mr$						
Higher Means Are:	Better						
Hypotheses:	$H_0: \delta \leq SM \text{ vs. } H_1: \delta > SM$						
Power	N1	N2	N	SM	$\delta$	$\sigma$	Alpha
0.98768	500	350	850	0	0.176	0.6	0.025

Power	The probability of rejecting a false null hypothesis when the alternative hypothesis is true.
N1 and N2	The number of items sampled from each population.
N	The total sample size. $N = N_1 + N_2$ .
SM	The magnitude of the margin of superiority. Since higher means are better, this value is positive and is the distance above the reference mean that is required to be considered superior.
$\delta$	The difference between the treatment and reference means at which power and sample size calculations are made. $\delta = \mu_1 - \mu_2 = Mt - Mr$ .
$\sigma$	The assumed population standard deviation for each of the two groups.
Alpha	The probability of rejecting a true null hypothesis. One-sided Alpha=0.025 that is equivalent to Two-sided Alpha=0.05

The null ( $H_0$ ) and alternative ( $H_1$ ) hypotheses for one-sided tests are defined as

$H_0: \mu_1 - \mu_2 \leq \delta_0$  versus  $H_1: \mu_1 - \mu_2 > \delta_0$   
or equivalently

$H_0: \delta \leq \delta_0$  versus  $H_1: \delta > \delta_0$ .

Rejecting this test implies that the mean difference is larger than the value  $\delta_0$ .

Superiority by a Margin tests are special cases of the above directional tests. It will be convenient to adopt the following specialized notation for the discussion of these tests.

#### Parameter Interpretation

$\mu_1$ : Mean of population 1. Population 1 is assumed to consist of those who have received the new vaccine.

$\mu_2$ : Mean of population 2. Population 2 is assumed to consist of those who have received the reference vaccine.

$MS$  (SM): Margin of superiority. This is a tolerance value that defines the magnitude of difference. This may be thought of as the smallest difference ( $>=0$ ).

$\delta$ : is the value of  $\mu_1 - \mu_2$ , the difference between the means. This is the value at which the power is calculated.

Note that the actual values of  $\mu_1$  and  $\mu_2$  are not needed. Only their difference is needed for power and sample size calculations.

#### Superiority by a Margin Tests

A superiority by a margin test tests that the treatment mean is better than the reference mean by more than the superiority margin. The actual direction of the hypothesis depends on the response variable being studied.

In this case, higher values are better. The hypotheses are arranged so that rejecting the null hypothesis implies that the treatment mean is greater than the reference mean by at least the margin of superiority.

The value of  $\delta$  at which power is calculated must be greater than  $|MS|$ . The null and alternative hypotheses with  $\delta_0 = |MS|$  are

$H_0: \mu_1 \leq \mu_2 + |MS|$  versus  $H_1: \mu_1 > \mu_2 + |MS|$

$H_0: \mu_1 - \mu_2 \leq |MS|$  versus  $H_1: \mu_1 - \mu_2 > |MS|$

$H_0: \delta \leq |MS|$  versus  $H_1: \delta > |MS|$

#### Objective 2

The coprimary noninferiority of the ARCT-2303 vaccine booster (groups 2a and 2b) compared to the ARCT-154 booster for the Omicron XBB.1.5 subvariant

Noninferiority (NI) of SCRARCT-2303 (booster) - SCRARCT-154

Statistical power for the coprimary objective 2 is calculated assuming that:

- the difference between SCR in ARCT-2303 (Day 29) and SCR in ARCT-154 (booster; ARCT154-J01 study) (Day 29) groups is expected to be  $>10\%$
- the SCR is equal to 50% in the ARCT-154 group

#### Non-Inferiority Tests for the Difference Between Two Proportions

##### Numeric Results

Solve For:	Power
Difference:	Z-Test with Unpooled Variance
Hypotheses:	$H_0: P_1 - P_2 \leq \delta_0$ vs. $H_1: P_1 - P_2 > \delta_0$

Power	N1	N2	N	Ref. P2	P1 H0 P1.0	P1 H1 P1.1	NI Diff $\delta_0$	Diff $\delta_1$	Alpha
0.99136	500	350	850	0.5	0.45	0.6	-0.05	0.1	0.025

\* Power was computed using the normal approximation method.

Power The probability of rejecting a false null hypothesis when the alternative hypothesis is true.

N1 and N2 The number of items sampled from each population.

N The total sample size.  $N = N1 + N2$ .

P2 The proportion for group 2, which is the standard, reference, or control group.

P1 The proportion for group 1, which is the treatment or experimental group.

P1.0 The smallest group 1 proportion that still yields a non-inferiority conclusion.  $P1.0 = P1|H0$ .

P1.1 The proportion for group 1 under the alternative hypothesis at which power and sample size calculations are made.  $P1.1 = P1|H1$ .

$\delta_0$  The non-inferiority difference under  $H0$ .  $\Delta_0 = P1.0 - P2$ .

$\delta_1$  The non-inferiority difference assumed by the alternative hypothesis,  $H1$ .  $\Delta_1 = P1.1 - P2$ .

Alpha The probability of rejecting a true null hypothesis. One-sided Alpha=0.025 that is equivalent to Two-sided Alpha=0.05

The two populations from which dichotomous (binary) responses are analyzed (the higher proportions are better) are investigational and control. The probability of response in population 1 (the new vaccine group: investigational) is  $p1$  and in population 2 (the reference group) is  $p2$ . Random samples of  $n1$  and  $n2$  individuals are obtained from these two populations. The data from these samples can be displayed in a 2-by-2 contingency table as follows.

	Success	Failure	Total
Investigational	$x_{11}$	$x_{12}$	$n_1$
Control	$x_{21}$	$x_{22}$	$n_2$
Totals	$m_1$	$m_2$	$N$

The binomial proportions,  $pp1$  and  $pp2$ , are estimated from these data using the formulae

$$\hat{p}_1 = x_{11}/n_1$$

$$\hat{p}_2 = x_{21}/n_2$$

Let  $p1.0$  represent the group 1 proportion tested by the null hypothesis,  $H0$ . The power of a test is computed at a specific value of the proportion which we will call  $p1.1$ . Let  $\delta_0$  represent the smallest difference (margin of non-inferiority that in our case is 0.05) between the two proportions that still results in the conclusion that the investigational agent is not inferior to the reference. For a non-inferiority test,  $\delta_0 < 0$ . The set of statistical hypotheses that are tested is

$H0: p1 - p2 \leq \delta_0$  versus  $H1: p1 - p2 > \delta_0$ , which can be rearranged to give

$H0: p1 \leq p2 + \delta_0$  versus  $H1: p1 > p2 + \delta_0$

The most direct is to simply give values for  $p2$  and  $p1.0$ . However, it is often more meaningful to give  $p2$  and then specify  $p1.0$  implicitly by specifying the difference.

Parameter	Computation	Hypotheses
Difference	$\delta_0 = p1.0 - p2$	$H0: p1 - p2 \leq \delta_0$ versus $H1: p1 - p2 > \delta_0$

